10.2 Bioelectrical impedance measurement

According to the physiological model of body composition, 5 compartments are defined (24) :

- Lean mass is the sum of water, bones and organs, excluding the fatty part. It is composed of :
 - The active cell mass (all the cells of the various organs and muscles);
 - Extracellular water (all interstitial fluids and plasma) ;
 - Bone mineral mass (tricalcium phosphate crystals in the skeleton) ;
- The fat mass corresponds to the triglycerides stored in the adipocytes, whatever their anatomical location; this compartment is virtually devoid of water.

Bioelectrical impedance measurement is based on the ability of hydrated tissue to conduct electrical energy. Impedance is a function of the volume of the hydro-electrolyte compartment in the body. The impedance (Z) of a body is related to the specific resistance (r), the length (L), and the conductive volume (V): $V = r L^2/Z$

According to the physiological model, fat mass is waterless and lean mass contains a fixed proportion (73%). From the estimated total body water, it is therefore easy to calculate the lean mass.

Water volumes (total body, extracellular, and intracellular) can be determined. Due to the characteristics of the current, the measurement is completely painless. When the current frequency is higher than 50 kHz, the measured volume is equal to the total body water. When the frequency is lower than 5 kHz, the volume is extracellular water. Measurements with several current frequencies allow an approach to the different water sectors.

Non-fat mass index and muscle mass index in kg/m² will be measured (see normal values in [Appendix 5](#)).

10.3 Morbidity and mortality criteria

10.3.1 Length of stay in hospital

The duration of hospitalisation is defined as the number of days of presence in the inclusion ward, from the patient's admission to the final discharge. Temporary transfers to another hospital department for an examination or an intervention are not considered as discharges.

A special statistical treatment (**described in section 11.4**) will be carried out on the length of hospital stay, given the impact of death on the length of stay.

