8.3 Impedance measurement bio-electrical

Bioelectrical impedance measurement is carried out in the patient's room using the Z-Metrix impedance meter from Bioparhom. The test is carried out when the patient is admitted to the ward.

The patient is positioned in the supine position, inclined at 30 degrees. The patient must rest for at least 15 minutes before the measurement. Four electrodes are placed:

- On the flat of the back of the hand;

- In the wrist at the level of the head of the ulna, in the intertendinous hollow;
- At the ankle, above the lateral malleolus ;
- Above the previous electrode, spaced about 4 fingerbreadths apart.

This non-invasive test quantifies muscle, lean and fat mass as well as bone and water mass. Values are expressed in kilograms and as a percentage of body weight (see measurement procedure in [**Appendix 5**](#)).

The following clues will be collected:

- Muscle mass index (in kg/m^2);
- Non-fat mass index (in kg/m^2).

9 Conduct of the research

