9.1.2 Sampling of the population

A potential of 94 patients per month eligible for this study are admitted in the short stay and follow-up care and rehabilitation of diabetology-obesity, pneumology, oncology and gastro-nutrition. We anticipate a maximum inclusion of 13 patients per month for logistical reasons. In order to obtain a representative sample of this patient population in the study, we will sample the patient population on admission , if they meet the eligibility criteria and before the patient is informed and consents are obtained. The patient will be randomly assigned to either the eligible or the ineligible group of the study. Patients in the ineligible group will therefore not be included in the study, but the number of such patients will be collected.

Patients will be sampled via a centralised randomisation system available via the internet, according to a pre-determined randomisation list. The randomisation list will be scheduled in advance by the study statistician. The sampling will be stratified on the care service, and unbalanced using random blocks in order to obtain a number of eligible patients of 15 patients per month (in order to take into account possible refusals of participation). Only the hospital research coordinator will know the randomisation list.

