9.2 Inclusion visit

The inclusion visit will take place within 48 hours of the patient or relative consenting to participate in the study. The following data will be collected:

- Age, weight, height, BMI, gender (male/female) ;
- Hospitalization service ;
- Reason for hospitalisation ;
- Background;
- Reduction in food intake or absorption ;
- Inflammatory situation ;
- Biological markers (albumin, pre-albumin, CRP) if applicable;
- Nutritional data (weight evolution over the last months, theoretical needs, ingestas) ;
- Mini-Nutritional Assessment Short-Form (MNA-SF);
- Autonomy score (Katz ADL) ;
- Bioelectrical impedance data ;
- Grip force (Handgrip) ;
- Walking speed.

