10.3.2 Mortality

Number of deaths out of the total number of patients included. A special statistical treatment (**described in section 11.4**) will be performed on the mortality rate.

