11.4.2 Comparison of morbidity and mortality

Morbidity and mortality will be compared between the HAS and GLIM groups, for moderate and severe undernutrition, by comparing the length of hospital stay, mortality and autonomy at discharge.

Length of stay in hospital

There is a relationship between the incidence of mortality and all length of stay variables. Length of stay will therefore be analysed using a competitive risk method, which takes into account the fact that patients who die are no longer eligible for length of stay analysis (25).

The estimator also provides the probability of in-hospital death, so that the probability of hospital discharge versus death at any time after inclusion in the study can be assessed simultaneously.

Mortality rate

The estimation of mortality rates will be carried out by the Kaplan and Meier method. The comparison of the 2 curves will be performed by a Logrank test. The mortality rates in the 2 groups will be estimated via the survival curves.

ADL

The ADL score will be compared between the 2 groups using the discrete numerical variable comparison tests described in the general aspects.

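### Length of stay has two time origins (admission in 10.3.1, inclusion in 11.4.2) and the mortality curves have none; if the admission-based duration is analysed unchanged, event-free days before consent count as time at risk

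*Combined protocol and SAP*

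**What the plan says.** - **Definition of stay (10.3.1).** Days present in the inclusion ward, "from the patient's admission to the final discharge". The section refers this same variable to section 11.4 because death affects length of stay.
- **Analysis of stay (11.4.2).** "Length of stay will therefore be analysed using a competitive risk method". The result is described so that "the probability of hospital discharge versus death at any time after inclusion in the study can be assessed simultaneously".
- **Mortality (10.3.2 and 11.4.2).** The measure is "Number of deaths out of the total number of patients included". Rates come from Kaplan-Meier curves: "The comparison of the 2 curves will be performed by a Logrank test". No time origin is given.
- **Entry into the study.** Section 9.1.2 says "we will sample the patient population on admission", before information and consent. Section 9.1.3 covers consent without limiting the time since admission. Section 9.2 adds: "The inclusion visit will take place within 48 hours of the patient or relative consenting to participate in the study".
- **Data collected.** Section 9.3 lists stay in days and vital status as yes or no. Section 4.2 names the date of death as an outcome. Neither 9.2 nor 9.3 lists an admission, consent or discharge date.

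**The concern.** Admission and inclusion are different moments, and the plan uses each as the start of the same analysis. A patient discharged or dead before consent is never in the sample, so every included patient was, by construction, still on the ward at consent. If the clock starts at admission and nothing else is done, the risk set holds days on which no event could have been seen. The curves start too flat, and early discharge and death probabilities are too low as estimates for patients admitted to these wards. Section 9.1.2 aims for a representative sample of that population.

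If the clock starts at inclusion, those days drop out, but the curve no longer describes the stay defined in 10.3.1. Either way an analyst must choose, and the plan leaves that choice open until the data are in hand.

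**Working it through.** The plan gives no figure for stay or mortality to reproduce. The first check is textual; the second sizes the effect under stated assumptions.

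**1. Which days are affected**

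| Interval | Can an event in an included patient be observed? | Counted under 10.3.1 | Counted from inclusion |
|---|---|---|---|
| Admission to consent | No: a patient who leaves or dies is never included | Yes | No |
| Consent to inclusion visit (at most 48 hours) | Yes: the end-of-research visit is at discharge or death | Yes | Depends on whether inclusion means consent or visit |
| After the inclusion visit | Yes | Yes | Yes |

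The event-free interval is therefore admission to consent. It counts as time at risk only if the 10.3.1 duration enters the estimator without an entry time.

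**2. Size for the absolute curves**

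Inputs:
- Mean stay about 30 days (section 6.3).
- Lag D from admission to consent: not given. D = 2 days is assumed, with 1 and 7 days as a range.
- Distribution of stay: not given. Two are assumed, both with mean 30: exponential, and lognormal with log-SD 1, so log-mean = ln 30 − 0.5 = 2.901.

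Let F(t) be the probability of having left the ward, by discharge or death, by day t.
- Share leaving before they could consent = F(D).
- Cumulative events by day t, admission origin, late entry ignored = [F(t) − F(D)] / [1 − F(D)], to be compared with F(t).

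Exponential, D = 2:
- F(2) = 1 − exp(−2/30) = 6.4%.
- F(7) = 1 − exp(−7/30) = 20.8%.
- Ignoring late entry: (0.2081 − 0.0645) / 0.9355 = 15.4%.
- Mean stay of those included: 30 + 2 = 32 days.

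Lognormal, D = 2:
- F(2) = Φ(0.693 − 2.901) = 1.4%.
- F(7) = Φ(1.946 − 2.901) = 17.0%.
- Ignoring late entry: (0.1697 − 0.0136) / 0.9864 = 15.8%.
- Mean stay of those included: 30.4 days.

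| D (days) | Stay | Leave before consent | Day 7: late entry ignored vs F(7) | Day 14: late entry ignored vs F(14) |
|---|---|---|---|---|
| 1 | Exponential | 3.3% | 18.1% vs 20.8% | 35.2% vs 37.3% |
| 1 | Lognormal | 0.2% | 16.8% vs 17.0% | 39.5% vs 39.7% |
| 2 | Exponential | 6.4% | 15.4% vs 20.8% | 33.0% vs 37.3% |
| 2 | Lognormal | 1.4% | 15.8% vs 17.0% | 38.8% vs 39.7% |
| 7 | Exponential | 20.8% | 0% vs 20.8% | 20.8% vs 37.3% |
| 7 | Lognormal | 17.0% | 0% vs 17.0% | 27.3% vs 39.7% |

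Simulation of 400,000 stays per case agrees to within simulation error (for D = 2: 15.3% vs 20.8%, and 15.8% vs 16.9%).

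**3. Size for a comparison of groups**

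One simulated sample per row: exponential stays, two separate groups, assumed discharge hazard ratio 0.70.

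| Lag | Admission origin, late entry ignored | Admission origin, left truncation |
|---|---|---|
| 2 days for everyone | 0.692 | 0.692 |
| Uniform 0 to 7 days in both groups | 0.685 | 0.687 |
| 1 day in one group, 4 in the other | 0.626 | 0.685 |

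The ratio moves only when the lag differs by group.

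**The case against.** The best defence is that 11.4.2 already speaks of time after inclusion. Curves that start there contain no event-free days, so the plan cannot be said to build the bias in. That stands: the bias is conditional. It does not remove the conflict, because 10.3.1 sends its own admission-based variable to that analysis and 9.3 collects stay only as a number of days.

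The gap may also be short. Patients are identified and sampled on admission, and for impedance "The test is carried out when the patient is admitted to the ward". This is why 2 days is a working assumption and 7 days an outer bound.

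A reader might infer more than the documents support:
- **That the unobservable window runs to the inclusion visit.** The 48 hours is a maximum that starts at consent, and an event after consent can be recorded, although some data needed for classification might be missing.
- **That a fixed share of admissions, such as 6%, is lost.** That figure depends on exponential stays; the lognormal with the same mean gives 1.4%.
- **That recorded stays are wrong.** For an included patient, admission to discharge is the true stay. The higher mean reflects who could be sampled.
- **That the HAS-GLIM comparison is biased.** Both definitions are applied to the same patients, so anyone positive on both carries the same lag into both groups. The documents show no lag that differs by nutritional status. Section 9.1.3 allows consent through a trusted person for confused patients, but 5.2 excludes incapacity to consent, and 9.1.3 does not make entry wait for the patient to recover.

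**Conclusion.** The concern holds as an unresolved specification. The plan gives two origins for length of stay, none for the mortality curves, and no handling of delayed entry. If the 10.3.1 duration is used unchanged, early cumulative incidence of discharge and death is understated.

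With an assumed 2-day lag and a 30-day mean stay, the day-7 shortfall is 5.4 percentage points for exponential stays (20.8 − 15.4) and 1.2 for lognormal stays (17.0 − 15.8). By day 14 it is 4.3 and 0.9 points. Both the lag and the shape of the distribution are assumptions, and the answer is sensitive to each.

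The documents do not support saying that the planned analysis is certainly biased, or that the HAS-GLIM contrast is materially affected. The primary outcome, prevalence compared by McNemar's test, uses no time origin and is untouched by this choice. This is a minor point about secondary outcomes, worth settling before analysis because it is cheap to settle.

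**What to change.** State one time origin in 10.3.1 and 11.4.2, covering length of stay and mortality.

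- **Preferred:** admission as origin, which keeps the 10.3.1 definition, with each patient entering the risk set at the date of consent (left truncation) in both the competing-risk and Kaplan-Meier estimators and in the log-rank test.
- **Alternative:** time from consent, with inclusion defined as consent, and total stay from admission reported descriptively.

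The clock should not start at the inclusion visit, because that would drop deaths and discharges between consent and visit.

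Add admission, consent, and discharge or death dates to the lists in 9.2 and 9.3. Section 9.1.3 already has consent recorded in the medical record, but the dates are not among the listed study data. Reporting the observed lag by nutritional group would show whether the contrast could be affected.

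The cost is a few date fields, a sentence in each section and a slightly different curve estimator. Left truncation also has limits. Early risk sets may be small, the curve before the earliest entry time cannot be estimated, and the method assumes that time of entry is unrelated to the later risk of discharge or death. The sample size and the primary analysis do not change.

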10.3.2 Mortality

Number of deaths out of the total number of patients included. A special statistical treatment (**described in section 11.4**) will be performed on the mortality rate.

10.3.3 Katz Activities Daily Living (ADL) score

The Katz ADL score (**Appendix 1**) is completed within 48 hours prior to (scheduled) discharge from hospital by the patient's nurse or nurse's aide. The total score is out of 6. A score of less than 3 indicates major dependence, a score of 0 indicates total dependence.

The Katz ADL score will be treated as a discrete numerical variable.

11 Statistical aspects

11.1 Calculation of the number of subjects needed

According to PMSI data, the prevalence of undernutrition according to HAS recommendations was 34%. Taking into account the wider period of weight loss and the higher BMI threshold used by GLIM in its definition of undernutrition, we estimate a higher prevalence of undernutrition. In the absence of data in the literature, we estimate a prevalence of undernutrition according to the GLIM definition at 49%, a difference of at least 15%. We wish to highlight this discrepancy. With a risk $\alpha = 0.05$ and a power of 80%, it will be necessary to include 260 patients.

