1.5 Convergences and divergences between the international and French definition

In adults under 70 years of age, both the GLIM and the HAS recommend screening for undernutrition, but the HAS recommendations do not recommend the use of a precise tool for assessing the risk of undernutrition. The presence of at least one aetiological criterion and one phenotypic criterion is mandatory to make a diagnosis of undernutrition in both situations. The differences between the international consensus and the HAS recommendations concern the diagnostic criteria used (Table 1).

Table 1: Comparison of the diagnostic criteria for undernutrition between the GLIM (1) and HAS definitions (7).

	Phenotypic criteria			Etiological criteria	
	Weight loss (%)	Low BMI (kg/m ²)	Reduction in muscle mass	Reduction in food intake or absorption	Inflammatory situation
GLIM	> 5% in the last 6 months or > 10% beyond 6 months	< 20	Reduction assessed by a validated measurement technique*.	≤ 50% of food intake > 1 week or any reduction > 2 weeks, or any gastrointestinal conditions or symptoms impacting assimilation or absorption	Acute or certain chronic or malignant conditions
HAS	≥ 5% in 1 month or ≥ 10% in 6 months or loss ≥ 10% from usual weight before onset of disease	< 18,5	Quantified Reduction** (QR)	Same as	Same as

* Methods of measuring muscle mass proposed by GLIM: Dual X-ray Absorptiometry (DEXA); bioelectrical impedance; CT or MRI. In the absence of these tools, anthropometric measurements such as arm or leg circumference can be used. Grip strength measurement is considered a complementary measure. The cut-off values are those of Cruz et al (14).

** Methods of measuring muscle mass proposed by the HAS:

³ Méthodes et seuils proposés selon les données les plus récentes à disposition

Méthodes de mesure	Hommes	Femmes
Force de préhension (dynamomètre) en kg	< 26	< 16
Vitesse de marche (m/s)	< 0,8	< 0,8
Indice de surface musculaire en L3 en cm ² /m ² (scanner, IRM)	52,4	38,5
Indice de masse musculaire en kg/m ² (impédancemétrie)	7,0	5,7
Indice de masse non grasse (impédancemétrie ^a) en kg/m ²	< 17	< 15
Masse musculaire appendiculaire (DEXA) en kg/m ²	7,23	5,67

The GLIM and HAS diagnostic criteria differ on the time period of weight loss, on the BMI cut-off values and on the tools for measuring muscle mass/strength/function.

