10.1 Prevalence of undernutrition

Undernutrition is defined according to the diagnostic methods of the HAS and GLIM:

	Phenotypic criteria			Etiological criteria	
	Weight loss (%)	Low BMI (kg/m ²)	Reduction in muscle mass	Reduction in food intake or absorption	Inflammatory situation
GLIM	> 5% in the last 6 months or > 10% beyond 6 months	< 20	Reduction assessed by a validated measurement technique*.	≤ 50% of food intake > 1 week or any reduction > 2 weeks, or any gastrointestinal conditions or symptoms impacting assimilation or absorption	Acute or certain chronic or malignant conditions
HAS	≥ 5% in 1 month or ≥ 10% in 6 months or loss ≥ 10% from usual weight before onset of disease	< 18,5	Quantified Reduction** (QR)	Same as	Same as

For the GLIM and HAS diagnostic method, the diagnosis of undernutrition is positive if an etiological criterion and a phenotypic criterion are present. The assessment of undernutrition according to GLIM will be preceded by a MNA-SF ([Appendix 4](#)). The methods for measuring the reduction in muscle mass are described in section "**7.2.4. Measurement of muscle function**".

Among patients with undernutrition, severe undernutrition is defined by :

	Moderate undernutrition	Severe undernutrition
GLIM	
 • BMI < 20 kg/m² • Weight loss of 5-10% in the last 6 months or 10-20% beyond 6 months • Mild to moderate reduction in muscle mass 	
 • BMI < 18.5 kg/m² • Weight loss of >10% in the last 6 months or >20% beyond 6 months • Severe reduction in muscle mass
HAS	
 • 17 < BMI < 18.5 kg/m² • Weight loss ≥ 5% in 1 month or ≥ 10% in 6 months or loss ≥ 10% from usual weight before onset of disease • Measurement of albumin by immuno-electrometry or immunoturbidimetry > 30 g/L and < 35 g/L. 	
 • BMI < 17 kg/m² • Weight loss ≥ 10% in 1 month or ≥ 15% in 6 months or loss ≥ 15% from usual weight before onset of disease • Measurement of albumin by immuno-electrodelemetry or immunoturbidimetry < 30 g/L

The prevalence of undernutrition is defined as the proportion of patients with moderate and/or severe undernutrition among the patients included in the study.

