11.2 General aspects

Descriptive statistics will be based on means (+/- standard deviation) or medians [interquartile range] depending on the distribution of quantitative variables. Qualitative variables will be described in terms of numbers and percentages. Univariate comparisons will use the usual statistical tests after checking the distribution of the variables (Chi2 or Fisher's test, t-test, anova or their non-parametric equivalents Wilcoxon and Kruskal-Wallis tests). Paired sample tests will be used if necessary.

The tests will be performed at the 5% significance level. The 95% confidence intervals will be provided for each estimate.

The calculations will be done using SPSS v21 IBM and R software (version 3.6.1, <http://www.R-project.org>).

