11.3 Main objective

The difference between the prevalences of global undernutrition between the HAS and GLIM groups will be compared using the McNemar test, designed for the comparison of proportions in matched samples.

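### The 80% power stated for 260 patients is not the power of the planned McNemar test: the discordant proportion is missing, and at 34% versus 49% power is about 92% or more unless the two diagnoses are negatively associated

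*Combined protocol and SAP*

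**What the plan says.** Section 11.1 takes the HAS prevalence as 34%, from the hospital's PMSI data. For GLIM, without published data, it says "we estimate a prevalence of undernutrition according to the GLIM definition at 49%, a difference of at least 15" (in percent). It expects GLIM to be higher for two reasons: "Taking into account the wider period of weight loss and the higher BMI threshold used by GLIM". At alpha 0.05 it concludes with "a power of 80%, it will be necessary to include 260 patients". It names no formula, sidedness, discordant proportion or correlation, and makes no allowance for patients who cannot be classified.

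Under section 11.3 the two prevalences are "compared using the McNemar test, designed for the comparison of proportions in matched samples". Section 11.2 adds: "The 95% confidence intervals will be provided for each estimate".

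On how the definitions overlap, section 1.5 says: "The presence of at least one aetiological criterion and one phenotypic criterion is mandatory to make a diagnosis of undernutrition in both situations". Table 1 gives the aetiological criteria as the same for both.

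**The concern.** McNemar uses only the discordant patients: those positive under HAS alone and those positive under GLIM alone. The margins of 34% and 49% fix the difference between these two shares at 15 points but not their sum, and power depends on the sum. So 80% power for 260 patients cannot be checked from section 11.1. If it does not describe the planned test, readers are misinformed about what the study can detect. That matters most when interpreting a gap below 15 points or a null result, since 49% is an admitted guess.

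**Working it through.** **Inputs.** HAS 0.34, GLIM 0.49, so d = 0.15; alpha 0.05; n = 260 (sections 11.1 and 11.2). Two-sided is assumed because the hypothesis in section 1.8 is non-directional. D is the discordant proportion: HAS-only = (D − d)/2, GLIM-only = (D + d)/2.

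**Where 260 might come from.** The document does not say.
- Two independent groups, two-sided: 332 (unpooled) to 338 (pooled) in total, or 364 with continuity correction. None matches.
- Two independent groups, one-sided: 262 (unpooled) to 266 (pooled). This is close, but it fits neither the paired analysis nor the hypothesis in 1.8.
- The recruitment target of 13 patients per month over 20 months also gives 13 × 20 = 260.

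Neither near-match shows what was done.

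**Range of D.**
- Nested (every HAS case is a GLIM case): D = 0.15.
- Independent: D = 0.34 × 0.51 + 0.49 × 0.66 = 0.1734 + 0.3234 = 0.4968.
- Largest the margins allow: D = 0.34 + 0.49 = 0.83.

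**Formulas.** Asymptotic power = Φ[(d√n − 1.96√D)/√(D − d²)]. N for 80% power = [1.96√D + 0.8416√(D − d²)]²/d². Exact power sums the two-sided conditional binomial test over a Binomial(n, D) number of discordant pairs. The 95% CI half-width is 1.96√((D − d²)/n).

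**Worked case, independence.** d√n = 0.15 × 16.125 = 2.419; 1.96√0.4968 = 1.381; √(0.4968 − 0.0225) = 0.689. Power = Φ[(2.419 − 1.381)/0.689] = Φ(1.506) = 93.4%. N for 80% = (1.381 + 0.580)²/0.0225 ≈ 171.

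Paired figures are asymptotic / exact. The 234-pair column assumes, for this review, that 10% of patients are unclassifiable (260 × 0.9).

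| D | HAS-only, GLIM-only | Power, 260 pairs | Power, 234 pairs | N for 80% | CI half-width at 260 (points) |
|---|---|---|---|---|---|
| 15% (nested) | 0%, 15% | >99.9% / >99.9% | >99.9% / >99.9% | 50 / 52 | 4.3 |
| 30% | 7.5%, 22.5% | 99.5% / 99.4% | 99.0% / 98.9% | 103 / 112 | 6.4 |
| 49.7% (independent) | 17.3%, 32.3% | 93.4% / 92.4% | 90.8% / 89.4% | 171 / 182 | 8.4 |

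**Where 80% would hold with 260 pairs.**
- Asymptotic: D = 0.752, HAS-only 30.1%. Then 30.1/34 = 88% of HAS-positive patients are GLIM-negative, and phi is −0.54. Exact power there is 78.1%.
- Exact: D = 0.719, HAS-only 28.4%. The share is 28.4/34 = 84%, and phi is −0.47.
- Under independence the share would be 17.34/34 = 51%.
- At the maximum, D = 0.83, power is 75.9% / 73.9%.

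**Is such discordance plausible?** The aetiological requirement is common to both definitions. A BMI below 18.5 is also below 20. The HAS weight-loss cut-offs lie within the GLIM ones apart from exact boundary values. These features point to positive association. HAS-only patients remain possible. HAS accepts grip strength and walking speed, whereas for GLIM "Grip strength measurement is considered a complementary measure". Section 10.1 also adds a screening step on one side only: "The assessment of undernutrition according to GLIM will be preceded by a MNA-SF". Nesting is therefore an optimistic bound.

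**Detectable difference, 260 pairs, 80% power** (HAS-only share assumed for this review): 7.2 / 7.5 points at 5% HAS-only; 9.4 / 9.7 points at 10%. Under independence with HAS at 34%: 12.1 / 12.4 points.

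**The case against.** First, this can be called an unstated assumption rather than a wrong number, because the margins permit a discordance at which 260 pairs give 80% power. That is arithmetically true. It needs definitions that disagree far more than unrelated ones would, against the plan's own criteria, so it does not rescue the statement.

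Second, the error is conservative only if the gap really is 15 points. This stands as a limit. At 34% versus 44%, exact power with 260 pairs is about 82% at 30% discordance and 61% under independence. The high power figures describe the plan's own assumptions and do not guarantee the study's performance.

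Third, sidedness is open: the summary and section 12 speak of verifying whether GLIM increases prevalence, and the nearest unpaired match to 260 is one-sided. A one-sided test would only raise McNemar power in the predicted direction, so 80% would be still further off. The plan should state which it uses.

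Fourth, the primary test is already the right paired one and no conclusion changes. That limits the seriousness, but the primary endpoint's sample-size justification still cannot be verified as written.

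**Conclusion.** The point holds. The stated 80% is not the two-sided McNemar power for 260 pairs at 34% versus 49%. Power is about 92% (exact, independence) to over 99.9% (nested), provided the diagnoses are not negatively associated and all 260 pairs are evaluable. With 234 pairs the lower end is 89.4%. The sample size, the choice of test and the type I error are unaffected. What is missing is a correct account of what 260 pairs can detect. It should be corrected, but it does not threaten the design.

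**What to change.** Keep 260. The margin over the 182 pairs needed for 80% exact power under independence is useful because 49% is a guess.

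In section 11.1:
1. State the assumed HAS-only and GLIM-only proportions.
2. Replace the 80% figure with McNemar power over that range, naming the test version (exact or asymptotic) and the number of evaluable pairs.
3. Write two-sided.
4. Add one scenario with a gap below 15 points. If a detectable difference is quoted, label it exact or asymptotic and give the HAS-only share.

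Possible wording, with illustrative splits for the sponsor to replace or justify:

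> At prevalences of 34% and 49%, 260 evaluable pairs give the two-sided exact McNemar test (alpha 0.05) 99.4% power if 7.5% of patients are HAS-only and 22.5% GLIM-only, and 92.4% if the diagnoses are independent (17.3% and 32.3%). With 234 pairs the figures are 98.9% and 89.4%.

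In section 11.3, specify that the 95% confidence interval promised in 11.2 is for the paired difference in prevalence, reported with the McNemar p-value.

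Cost: one paragraph in 11.1 and one clause in 11.3, with no extra patients, data or procedures.
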